New Computerized Behavioral Task: Research assistants will administer a new computerized behavioral task to assess intent to engage in healthy behaviors via measurement of time spent by youth (in seconds) and engagement (measured in number of clicks) with a social media platform. During online administration the research assistant will send the participant a link to the website and ask the participant to share their screen while they are viewing the website. Unlike other measures, this computerized measure captures the amount of engagement with a health-promoting social media platform as our behavioral outcome. The interviewer will show the participant the website, developed by our team to be educational and interactive. The computerized behavioral task will be presented while participants are being asked to consider the hypothetical genetic malleability framing. The website has these sections: i) Information on ways to improve mental health; ii) Ways to find help; and iii) Social support blog, which offers access to an online support community of other youth with psychotic symptoms. Each section has options for the viewer to click and read. Using Google Analytics, a website feature, we will capture metrics for each participant such as: 1) the time in seconds the participant spends on each page, and; 2) the number of interactions with the website. This computerized measure promises to expand measurement of behavioral intention in a novel way, thus capturing an important new element of health-promoting behavioral change.

Acceptability assessment. Acceptability of each educational session will be assessed via audiotaped individual interviews wherein youth will be asked to "think aloud" about the content of the educational session. Youth will be queried regarding their cognitive processes about the educational session. Youth will be asked to report their understanding and any other cognitive process surrounding the overall content of the educational session. The following questions will be asked as part of the acceptability assessment.

Can you tell me what you think the educational session is about? (open ended question)
What did you learn? (open ended question)

What did you think about the educational session? (open ended question)

Follow-up question: Were you able to understand it? (open ended question)

Follow-up question: Was there anything that was confusing to you? (open ended question)

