Follow-up question: Is there anything you would change? (open ended question)

Did you understand that this session was about genetic malleability, or the idea that genes may put someone at risk to develop psychosis but there are environmental or lifestyle factors that can keep the gene from turning on? Answer choices: Yes/No

Further, participants will be asked to complete a brief usability questionnaire. If stress is indicated at any point regarding interacting with the tool or clinician, participants will be carefully probed for the source of any stress or adverse and serious adverse events, and will be immediately referred to a clinician, either [name] (the director of COPE), [name] (chief psychologist at COPE), or our clinician who is administering our clinician manual ([name]).

Debriefing: Immediately following completion of the post- educational session assessments, participants will be debriefed (1st debriefing) via: (1) discussing any concern about the genetic framing; (2) reinforcing that while researchers are beginning to identify genes that combine with each other to increase risk of development to psychosis, the genetic framing is hypothetical (that no clear genetic markers or biological tests yet exist for psychosis) followed by a True/False quiz testing knowledge of the current state of genetics in psychosis (described below); and (3) identifying distress via a distress protocol (see below) and an adverse and

serious adverse event (SAE) checklist (see below). To ensure that participants understand that the genetic framing is hypothetical, each participant will be asked 8 True/False questions following being told that the situation is hypothetical (e.g., “Currently, genes only suggest that a person may be at a higher risk of developing psychosis. It does not mean that he or she would definitely get the disorder”). Respondents will answer each question, and the interviewer will discuss any item that the respondent gets wrong to ensure understanding.

A second debriefing will occur 2-weeks after study completion, and again at 3-months after study completion. If any distress or adverse reaction is found, referral to [name], [name], or [name] will occur immediately.

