2) Second, interviewers will ask semi-structured, open-ended questions at the end of the interview to assess distress due to the study procedures (see below).

Due to your participation in this study, please answer “yes” or “no” the following questions.

1. Are you experiencing a high level of stress or emotional distress?
2. Are you currently having thoughts of harming yourself?
3. Are you currently having thoughts of harming someone else?

If participants answer “yes” to any of the above questions they will be referred to a clinician.

3) Third, interviewers will be trained to pay attention to crying, shaking, agitation (pacing, breaking away from the task) during the interview. RA’s will have completed or will be actively completing a clinical placement at COPE. If participants exhibit distress during exposure to the tool/interview, interviewers will stop the study procedures and ask if participants would like to discontinue the study. If so, the participant will be removed from the study and immediately referred to a clinician.

In sum, participants will indicate a “positive” distress rating on the “Distress Protocol” if they: 1) score “positive” on the quantitative items (see above); 2) respond affirmatively to the semi-structured, open-ended questions following all study procedures (see above); 3) exhibit distress during exposure to the tool/interview. If participants rate “negative” on all three components, participants will still be asked if they would like to check in with a clinician.

****All participants regardless of whether they demonstrate any distress during the protocol will also be asked the below questions after completion of all study procedures as part of the debriefing protocol:**

True/False Quiz Administered As Part of Debriefing Protocol

- 1) There currently exists a blood test to identify genetic risk for psychosis (F)
- 2) Scientists have identified genes that definitely cause psychosis (F)
- 3) Only genes determine one's chance of developing psychosis (F)
- 4) If you have a genetic risk for psychosis, this means that you will definitely develop psychosis (F).
- 5) Currently, genes only suggest that a person may be at a higher risk of developing psychosis. It does not mean that he or she would definitely get the disorder. (T)
- 6) The situation that we presented to you today about a blood test for psychosis was not real (T)
- 7) Psychosis may be caused by many factors, and genes could be one of them. (T)

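### The one closed question in the acceptability interview states its own answer, so a yes cannot show that the message was understood

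*Combined protocol and SAP*

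**What the plan says.** Section 2 (Objectives) makes initial acceptability of each tool one of the things the study is to establish. Section 4 (Study Design) has the acceptability measures given once, after the post-test measures.

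Section 5 (Acceptability assessment) describes a recorded think-aloud interview in which understanding is part of the purpose: "Youth will be asked to report their understanding and any other cognitive process surrounding the overall content of the educational session". The interview opens with "Can you tell me what you think the educational session is about? (open ended question" and "What did you learn? (open ended question". Further questions, also labelled open ended, ask for the participant's opinion of the session, whether it could be followed, what was confusing and what should change.

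One closed question comes after these. It begins "Did you understand that this session was about genetic malleability, or the idea that genes may put someone at risk to develop psychosis" and ends "but there are environmental or lifestyle factors that can keep the gene from turning on? Answer choices: Yes/No". A usability questionnaire follows, but its items are not printed.

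Debriefing comes next. There "each participant will be asked 8 True/False questions following being told that the situation is hypothetical", and the exercise is described as a "True/False quiz testing knowledge of the current state of genetics in psychosis". The interviewer discusses any wrong answer. Item 4 is an example: "If you have a genetic risk for psychosis, this means that you will definitely develop psychosis (F", so the keyed answer is False.

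Section 6 (Statistical Analysis Plan) covers the pre versus post comparisons and their stratification. It does not mention acceptability or comprehension.

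**The concern.** The closed question supplies the definition of genetic malleability and then asks whether the participant understood that this was the topic. A participant who took nothing from the session can truthfully say yes once the question has been read out. The item also concerns recognising a topic rather than grasping an idea.

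A Yes/No count is the easiest acceptability figure to tabulate. If it were reported as the share who understood, a tool that failed to convey its message could look much like one that succeeded. Section 5 notes that this population shows some cognitive impairment and sets the text at an 8th grade level, so failure to understand is a risk that the protocol itself recognises. The timeline puts refinement of the tools after testing, and Section 3 looks ahead to a randomised trial. A communication failure should therefore be visible at this stage.

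**Working it through.** The plan gives no expected yes-rate, pass mark or scoring rule for this item, so there is no figure to reproduce. The check is a reading of the order of events, followed by an illustration with assumed inputs.

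**1. What measures understanding after the session, in order (Section 5).**
- Post-test measures repeat the pre-test set apart from a short list of pre-only measures. Genetic essentialism is not on that list, so it is measured again. It captures belief rather than knowledge.
- The open-ended acceptability questions are unprompted and recorded. No coding rule is stated.
- The leading Yes/No item.
- Debriefing, then the eight keyed True/False items. Items 3, 4, 5 and 8 overlap the malleability message, but by then the facts have been explained.

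The leading item is therefore the only closed comprehension item printed before debriefing.

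**2. What a yes-rate would mean.** Let u be the share who truly understood and a the chance that someone who did not understand still says yes. Both are assumptions. If everyone who understood says yes, then

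P(yes) = u + (1 − u)a, and the overstatement is (1 − u)a.

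| u | a | P(yes) | Overstatement |
|---|---|---|---|
| 0.60 | 0.5 | 0.60 + 0.40 × 0.5 = 0.80 | 20 points |
| 0.80 | 0.5 | 0.80 + 0.20 × 0.5 = 0.90 | 10 points |
| 0.60 | 0.9 | 0.60 + 0.40 × 0.9 = 0.96 | 36 points |
| 0.80 | 0.9 | 0.80 + 0.20 × 0.9 = 0.98 | 18 points |

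A difference in true comprehension is shrunk by the factor (1 − a). At a = 0.9, the 20-point gap between u = 0.60 and u = 0.80 appears as 2 points. One participant in 27 is 1/27 = 3.7 points.

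**3. What 27 participants per tool would show.** With u = 0.50, the binomial chance of at least 25 yes answers out of 27 is:
- a = 0: P(yes) = 0.50, chance below 0.001
- a = 0.5: P(yes) = 0.75, chance 0.02
- a = 0.8: P(yes) = 0.90, chance 0.49
- a = 0.9: P(yes) = 0.95, chance 0.85

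The result turns on a, which the documents do not give.

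**4. A unanimous result.** For 27 yes out of 27 the exact 95% lower limit is 0.025^(1/27) = 0.87. That limit is for the yes-rate. It puts no bound on understanding.

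**5. Check on the replacement items.** If those who do not know guess at 50%, a single True/False item reads 0.60 + 0.40 × 0.5 = 0.80 to 0.80 + 0.20 × 0.5 = 0.90, which is still 10–20 points high. If guesses are independent, all three are guessed correctly with chance 0.5³ = 0.125. The share with all three correct is then 0.60 + 0.40 × 0.125 = 0.65 to 0.80 + 0.20 × 0.125 = 0.825, or 2.5–5 points high. Items 3 and 4 are keyed False, so a participant who agrees with everything fails them.

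**The case against.** The strongest reply is that the interview does not depend on this question. Two unprompted, recorded questions come first and could be scored. Genetic essentialism, defined in Section 3 as beliefs of permanence and inevitability, is re-measured before debriefing against a baseline, and it bears on whether the message was taken up. Eight keyed items follow at debriefing. No threshold, success criterion or planned claim is tied to the Yes/No item, which is neither a primary nor a secondary outcome.

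Most of this stands, and it rules out three stronger readings that a reader might infer:
- *That comprehension is otherwise unmeasured.* The open-ended questions are there. What they lack is a coding rule. The unprinted usability questionnaire cannot be assumed to have no comprehension items.
- *That nearly everyone will say yes.* This is plausible, but no document gives a rate, and step 3 of the working shows how much depends on the assumed one.
- *That the study will claim near-universal comprehension.* The plan states no such use of the item.

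The reply does not rescue the item itself. The other sources can show understanding, but a yes to a question that contains its answer adds nothing to them. The quiz cannot fill the gap because it follows explanation, and its stated purpose is knowledge of the current science and of the framing being hypothetical.

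**Conclusion.** The item is leading, and a yes to it should not be cited as evidence of comprehension. That follows from the wording and needs no numerical assumption. The size of any overstatement cannot be taken from the documents. With true comprehension assumed at 60–80%, it runs from 10–20 points (50% of non-comprehenders agreeing) to 18–36 points (90% agreeing), and it falls to zero if none of them agree.

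The consequence is limited. The pre versus post analyses are untouched and no decision depends on the answer. This is a worthwhile, inexpensive improvement to how acceptability is assessed, not a threat to the trial's main results.

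**What to change.** Replace the Yes/No item with closed items that do not supply the answer. Existing quiz items 3 (genes alone decide), 4 (genetic risk means certainty) and 8 (environment or lifestyle affects how genes work) would serve. None of them reveals that the situation is hypothetical, as items 1, 2 and 6 could.

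Ask them after all post-test outcome measures and after the open-ended acceptability questions, but before debriefing. Placing them straight after the tool would put them ahead of the outcome measures. That could prime those measures and would depart from the order in Section 4.

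Report the proportion correct for each tool (n=27) with an exact binomial interval, by item and for all three together. Present it beside the answers on what the session was about and what was learned, with a short coding rule for those answers fixed in advance. Keep the full eight-item quiz at debriefing unchanged, since it protects participants.

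Costs: about one minute per participant, and three items seen twice. True/False answers can be guessed, and item 8, keyed True, is also open to yes-saying. With no baseline, the result describes understanding after the session and not gain from the tool. If the sponsor prefers no new items, the minimum is to drop the Yes/No count as evidence and rest comprehension on the coded open-ended answers.

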6. STATISTICAL ANALYSIS PLAN

We will assess variables’ distributions. We use bivariate tests to compare pre- vs post-intervention outcomes via paired t-test and Mann-Whitney Signed Rank tests. Primary and secondary outcomes will be assessed. We will stratify the sample by key covariates (e.g., IQ) and test for significant pre- vs post-mean difference scores by stratification.

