4. METHODS

Study Design

The study will be rolled out in two phases:

- (1) development of the translational tools; and
- (2) assessment and evaluation of the safety, acceptability and effectiveness of tools using pre-post comparisons.

A sequential assignment procedure will be used to assign participants to first the Clinician Manual educational session and then the PsyGist educational session. Thus, the first 27 individuals enrolled in the study will be assigned to the Clinician Manual educational session, while the next 27 individuals will be assigned to the PsyGist educational session (Clinician Manual n=27; PsyGist n=27; Total N=54). Sequential assignment is being utilized in this protocol to ensure that the probability of contamination, resulting from participants sharing study information between educational session groups, is minimized.

All Assessments will be presented in two 2.5-hour visits, 1 week prior and immediately after exposure to each Tool (Clinician Manual or PsyGist) because it would be unethical not to debrief youth about the hypothetical framing immediately following the session. However, we will take as many brief breaks throughout the sessions as necessary to accommodate the participant. 'Acceptability' measures will be administered only once after post-test measures.

Inclusion and Exclusion Criteria

All subjects will be drawn from the Center for Prevention and Evaluation Criteria (COPE's) Clinical High Risk for Psychosis (CHR) participants at the New York State Psychiatric Hospital (see protocol information below).

THE CENTER OF PREVENTION AND EVALUATION (COPE): A PROSPECTIVE STUDY OF SYMPTOMS AND COGNITION (FORMERLY 5567R) PI: [name] (Protocol Number: 6654R)

Below are the overall inclusion criteria for the Center for Prevention and Evaluation Criteria (COPE), which is the recruitment site. Note that below we have specific recruitment criteria that identify a subset of the COPE respondents.

INCLUSION CRITERIA	METHOD OF ASCERTAINMENT
1. Male or females between the ages of 14-30	Phone screen and interview
2. Capacity to give informed consent for participants 18 and over OR participant's assent plus informed consent from parent for participants under the age of 18	Interview; assessment by clinician not involved in the study
3. English-speaking (for participants)	Phone screen and interview

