 - Will not be included in this study
- Prisoners
 - Will not be included in this study

Description of Subject Population:

All subjects will be recruited from The Center for Prevention and Evaluation's (COPE) prodromal population at The New York State Psychiatric Institute (NYSPI).

Population to be Recruited: Individuals at Risk for Psychosis (CHR)

Number of completers required to accomplish study aims: $n=27$ /tool (PsyGist & Clinician Manual); $N=54$ total participants between both groups (PsyGist & Clinician Manual)
Projected number of subjects who will be enrolled to obtain required number of completers: $N=100$

Age range of subject population: 16-30 years old

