Regarding discontinuation criteria and who will determine if a participant is too ill to continue to participate, a participant will discontinue the study under the following conditions: (1) if the participant decides not to continue the study for personal reasons; and (2) if the patient presents with acute or imminent harm to themselves or others, or suffers other incapacitating conditions (i.e., exacerbation of prodromal psychosis symptoms to the point of requiring in patient hospitalization) he or she may be removed from the study; and (3) if the participant develops full symptoms due to psychosis. In all cases, the participant's treating clinician will consult with the PI and be informed about the discontinuation of study participation.

Data Safety and Monitoring Board:

Given that the proposed study is an NIH-defined Phase I clinical trial, and that we are recruiting children, a Data and Safety Monitoring Board will be appointed. Members of the DSMB will include three established and well-recognized experts in stigma and psychosis/CHR who are doctoral-level clinicians and researchers who have had at least 5 years of clinical experience working with psychosis/CHR. The following members will comprise the DSMB, all of whom have no affiliation or role in the project: [name], [name], and [name]. The DSMB will convene every six months and in the event of a serious adverse event.

Review/monitoring activities will include reviewing the protocol, risk-benefit considerations, informed consent documents and plans for data safety and monitoring; evaluating the progress of the study, including periodic assessments of data quality and timeliness, participant recruitment, accrual and retention; and other factors that can affect study outcomes; considering factors external to the study such as scientific or therapeutic developments that may have an impact on the safety of the participants; protecting the safety of the study participants and reporting on the safety and scientific progress of the trial. In addition to having the power to recommend to the PI that the study be stopped or modified, the DSMB can determine whether

any adverse event or serious adverse event affects the risk-benefit ratio of the study, and whether modifications to the protocol or consent forms are required.

REFERENCES:

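### The paired pre-post tests omit anyone who becomes distressed during the tool and chooses to stop, so the completer result could be biased, probably toward benefit

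*Combined protocol and SAP*

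**What the plan says.** - **Analysis (section 6).** "We use bivariate tests to compare pre- vs post-intervention outcomes via paired t-test"; a signed-rank test is named alongside it. The section also mentions checking distributions and stratifying by covariates. It states no analysis population, no rule for a missing score and no sensitivity analysis, and no other section supplies them.
- **Timing (section 4, Study Design).** Assessments are made "1 week prior and immediately after exposure to each Tool". The contacts at 2 weeks and 3 months in section 5 are debriefings, so no later efficacy score could replace a missing one.
- **Distress during the tool (section 5, Distress Protocol, third component).** When distress is seen, "interviewers will stop the study procedures and ask if participants would like to discontinue the study". For a participant who answers yes, the consequence is stated next: "If so, the participant will be removed from the study and immediately referred to a clinician".
- **Other exits (section 7, Discontinuation criteria).** "a participant will discontinue the study under the following conditions": personal reasons, acute or imminent harm or an incapacitating condition ("he or she may be removed from the study"), or full psychosis.
- **Sample (section 4, Description of Subject Population).** The requirement is 27 completers per tool, 54 in all. "Projected number of subjects who will be enrolled to obtain required number of completers" is given as 100.
- **Design (section 2).** Nonrandomised, within-subject, pre versus post for each tool, with no control arm.

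**The concern.** Each rule is unremarkable alone. Together they select on reaction to the tool. A participant who is upset by the session and stops has a pre score and no post score, cannot enter a paired test, and does not count toward the 27. Recruitment to a completer target in effect replaces that person. A tool that some participants could not tolerate could therefore still deliver a full set of 27 pairs drawn from those who tolerated it, and no control arm would show the selection.

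Section 2 contrasts fatalistic acceptance with proactive preventive behaviour. If people who stop in distress lean toward the first, their intent and stigma changes would have been less favourable than those of completers, and the completer mean would overstate benefit. Section 3 says that confirming the tools' utility would give a basis for a later randomised trial, so an overstated effect would carry forward.

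**Working it through.** **Inputs from the documents.** 27 completers per tool, 54 in total, 100 projected enrolments (section 4); paired t-test (section 6).

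**Inputs assumed, because the documents give none.** Two-sided alpha 0.05; SD of change 1; completer mean change 0.50 SD, scored so that positive is favourable; the number of leavers k and their change c.

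**1. The plan's own figures.** The target of 27 cannot be reproduced, since no alpha, power, effect size or SD is stated. For orientation, 27 pairs give 80% power at an effect of 0.56 SD (two-sided 0.05). Projected non-completion is 100 - 54 = 46, or 23 per tool if split evenly. No reasons are given, and some of these losses may come before the tool. It is therefore a ceiling on tool-related loss, not an estimate.

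**2. Completers alone.** t = 0.50 × √27 = 2.60 on 26 df, p = 0.015; 95% interval 0.10 to 0.90.

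**3. Adding back k leavers, each with change c.**

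n = 27 + k; mean = (27 × 0.50 + k × c)/n; sum of squares = 26 + 27 × 0.25 + k × c²; SD² = (sum of squares - n × mean²)/(n - 1); t = mean × √n/SD.

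For k = 3 and c = -1: mean = (13.5 - 3)/30 = 0.35. Sum of squares = 26 + 6.75 + 3 = 35.75. SD² = (35.75 - 30 × 0.1225)/29 = 1.106, so SD = 1.052. t = 0.35 × √30/1.052 = 1.82 on 29 df, p = 0.079.

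| Leavers k | Change c (SD) | Mean (SD) | 95% interval | p |
|---|---|---|---|---|
| 0 | n/a | 0.50 | 0.10 to 0.90 | 0.015 |
| 2 | -1 | 0.40 | 0.00 to 0.79 | 0.049 |
| 3 | -1 | 0.35 | -0.04 to 0.74 | 0.079 |
| 5 | -1 | 0.27 | -0.12 to 0.65 | 0.17 |
| 3 | -0.5 | 0.40 | 0.03 to 0.77 | 0.036 |
| 5 | -0.5 | 0.34 | -0.01 to 0.70 | 0.058 |
| 10 | -0.5 | 0.23 | -0.09 to 0.55 | 0.155 |
| 5 | 0 | 0.42 | 0.08 to 0.76 | 0.016 |
| 23 | 0 | 0.27 | 0.05 to 0.49 | 0.017 |

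The lower limit for 2 leavers at -1 SD is just above zero (0.002).

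The last two rows matter for the remedy. Adding zeros lowers the mean but also shrinks the SD and raises n, so p hardly moves even when the estimate nearly halves. A zero-change analysis alone would not test the significance claim.

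**4. If the tool had no effect at all.** Suppose true mean change among everyone exposed is zero and a share q stops. If stopping depends on distress, and distress has correlation ρ with change, the completer mean is -ρ × φ(z)/(1 - q), where z is the cut-off that removes the share q and φ is the normal density. The ratio φ(z)/(1 - q) is 0.103/0.95 = 0.11 at 5%, 0.175/0.90 = 0.195 at 10% and 0.280/0.80 = 0.35 at 20%.

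| Correlation ρ | 5% stop | 10% stop | 20% stop |
|---|---|---|---|
| -1 (worst changers stop) | 0.11 | 0.195 | 0.35 |
| -0.5 | 0.05 | 0.10 | 0.18 |
| -0.3 | 0.03 | 0.06 | 0.11 |
| 0 | 0 | 0 | 0 |
| +0.3 | -0.03 | -0.06 | -0.11 |

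In the extreme first row, simulation (20,000 runs, 27 completers) puts the chance of a significant result in the tool's favour at about 7%, 18% and 64%, against a nominal 2.5%. Under moderate correlations the spurious gain is much smaller.

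**The case against.** Several stronger readings are tempting, and the documents do not support them.

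- **That everyone distressed is lost.** Removal follows only if the participant opts to stop. Those who continue keep their post score, and distress found by the rating scale or the closing questions leads to referral, not removal.
- **That the bias is certain and favours the tool.** The tested outcomes are intent and stigma; distress is a separate safety measure. No section says that distressed leavers would have changed less favourably. The bias is zero at correlation 0 and reverses if distress goes with higher intent.
- **That the section 7 exits are also reactions to the tool.** The pre score is a week before exposure and the post score immediately after it. Most of the time in which such an exit could cost a pair therefore lies before the tool.
- **That 46 of 100 measures tool-related loss.** It may include ineligible people and those lost in the pre-tool week. Section 4 also assigns the first 27 and next 27 individuals enrolled, so the meaning of enrolled is itself unsettled.
- **That safety rates are computed on completers.** The distress protocol runs through all phases, and adverse-event reporting has no completion condition. Leavers are absent from the efficacy test, not from safety reporting. Acceptability is assessed only after the post-test, so early stoppers miss it, but it is mainly open-ended and no rate is planned.

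It is also fair to say that one leaver at -1 SD leaves p at 0.029, and that this is an early-phase tool-development study. These objections limit the size and certainty of the point. They do not supply the missing analysis set, or a rule for someone who starts the tool and has no post score.

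**Conclusion.** The point holds in a limited form. The stated rules leave out of the efficacy result anyone who becomes distressed during the tool and chooses to stop, and the completer target in effect replaces them. The result could be biased, probably toward benefit, on the condition that leavers would have changed less favourably than completers. That condition is plausible but is not shown in the documents.

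The size is unknown because no expected number of such exits is given. With an assumed completer effect of 0.50 SD, three leavers at -1 SD or five at -0.5 SD are enough to take p above 0.05; two at -1 SD are borderline; leavers at zero change make almost no difference to p. The plan should be changed, with medium confidence in the practical effect.

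**What to change.** In section 6, leaving the removal rule unchanged:

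1. Define the analysis set for each tool as everyone who starts the tool session.
2. Tabulate enrolled, started and completed by tool, with reasons for each loss and whether it came before or after the session began.
3. Use starters as the denominator for any distress or adverse-event rate, and report how many starters did not reach the acceptability assessment.
4. Keep the paired test on available pairs as the main analysis. Add a prespecified sensitivity analysis that gives starters without a post score a range of unfavourable changes, for example -0.5 and -1 SD, or a tipping point. Sign the change by outcome, since lower stigma is favourable. Do not rely on zero change alone.
5. Report the estimate and interval as well as p, because a single assigned value distorts the SD. If the result does not hold, describe the main result as applying to completers.

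The cost is a few sentences of SAP text, one participant-flow table and one extra analysis, with no new participants or visits. The reported effect may look less favourable.
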